3. STUDY PLAN AND PROCEDURES

3.1 Overall study design and flow chart

This is an 8 week, randomised, double blind, double dummy, national, multicentre study with 3 parallel treatment groups: rosuvastatin 10 mg, rosuvastatin 20 mg and placebo. The primary end point of the study is the change in triglycerides levels from baseline to week 8. Approximately 10 to 12 centres will be required in order to recruit 330 randomised patients, of whom 285 to 300 are expected to be fully evaluable (i.e., to allow for approximately 10 to 15% of randomised patients being non-evaluable). The approximate numbers of randomised patients will be recruited from Mexico City (150 patients), Monterrey (90 patients), Guadalajara (60 patients), Toluca (30 patients) and San Luis Potosi (30 patients). It is anticipated that in order to achieve this number of randomised patients, approximately 990 patients will need to enter the lead-in period of the study (screen failure rate 3:1). Centres will be required to randomise approximately 30 patients each. Centres may be discontinued from the study if recruitment rates are poor and new centres may be added if necessary to achieve recruitment goals. Recruitment will be competitive across cities and centres (thus, centres numbers are approximate). There is no maximum number of patients that centres can recruit. and centres will stop enrolment once enough patients are screened to provide the projected number randomised.

There are 4 clinic visits planned. Visit 1 and 2 occurs during the lead-in period. Visit 2.1 is the randomisation visit, and Visit 3 occurs during the randomised treatment period, is the final visit. For visit 1, the allowed window will be ± 3 days, for visit 2 the allowed visit window will be ± 3 days. For visit 2.1 the allowed visit window will be ± 2 day and for visit 3 the allowed visit window will be ± 3 days.

Male and female patients aged ≥ 18 with hypertriglyceridemia (HTG) and statin naïve (as defined by protocol) will be recruited. Patients will then enter a 4-week lead-in period during which they will undergo TLC dietary advice (see Appendix F) and no lipid lowering therapy will be allowed. All eligible patients will be randomised in a 1:1:1 ratio to receive ether rosuvastatin 10 or 20 mg/day or placebo once a day. Patients will be followed for 8 weeks. All patients will be offered the opportunity to continue with active commercially available therapy with rosuvastatin once the protocol is complete.

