^d Review and titrate if necessary patient's anti-hypertensive medication, to an individually optimised dose to a blood pressure target of <130/80 mmHg based JNCVII guidelines and investigator discretion.

^e Patients should fulfil all inclusion criterion with no exclusion criterion to continue in the study during visit 1, 2 and 2.1.

^f Lipid profile: TG, LDL-C, TC, HDL-C, nonHDL-C, TC/HDL-C, LDL-C/HDL-C and non-HDL-C/HDL-C ^g Apolipoprotein analysis to include ApoA-1, ApoB, ApoB/ApoA-1 ratio

^h Urinalysis will consist of: visual description (colour and appearance), a dipstick test (specific gravity, pH, protein (qualitative), haematuria, glucose, ketones, bilirubin and blood), microscopy (red blood cells, white blood cells, bacteria, casts and crystals.

^j Reduced hepatic profile will consist of: ALT, AST and GGT

^k Complete hepatic profile will consist of: total bilirubin, ALT, AST, alkaline phosphatase and gamma-glutamyl transferase (GGT)

¹An assay of B-HCG will only be performed at visit 1 for women of childbearing potential.

^m SAEs should be followed up for 30 days after the last dosing of study treatment

ⁿ Patients will be randomised once the laboratory results from visit 2 are available. Study drug will be dispensed at visit 2.1.

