3.3.3 Exclusion criteria

Any of the following is regarded as a criterion for exclusion from the study:

- 1. LDL-C levels \geq 190 mg/dL
- 2. History of any other lipid lowering therapy 6 months before visit 1.
- 3. Subjects considered to be unstable after a myocardial infarction, unstable angina, myocardial revascularisation or a transient ischemic attack (TIA) or stroke
- 4. Subjects awaiting a planned myocardial revascularization prior to starting the study (ie, planned prior to visit 1)
- 5. Severe congestive cardiac failure (New York Heart Association [NYHA] Class IIIb or IV)
- 6. Uncontrolled diabetes diagnosis by $HbA_{1c} \ge 8\%$, or fasten oral glucose $\ge 150 \text{mg/dL}$.
- 7. History of malignancy (unless a documented disease-free period exceeding 5 years is present) with the exception of basal cell or squamous cell carcinoma of the skin. Women with a history of cervical dysplasia would be permitted to enter the study provided they have 3 consecutive clear Papanicolaou (Pap) smears.
- 8. Uncontrolled hypothyroidism defined as a thyroid stimulating hormone (TSH) >1.5 times the upper limit of normal (ULN) at Visit 1. (This is due to the relationship between myopathy and patients with hypothyroidism undergoing statin therapy)
- 9. History of homozygous familial hypercholesterolaemia. (Due to the lipid levels exhibited by this group of patients they are considered unsuitable for this study as they often require combination lipid-lowering therapy)
- 10. History of alcohol, or drug abuse within the last 5 years.
- 11. Current active liver disease [alanine aminotransferase (ALT) (SGPT) > 3 x ULN] or severe hepatic impairment
- 12. Unexplained rise of creatine kinase (CK) \ge 3 x ULN at visit 1

- 13. Serum creatinine > 176 μ mol/L (2.0 mg/dL) at visit 1
- 14. Pregnancy, breast-feeding, and women of childbearing potential who are not using a reliable contraception method.
- 15. Subjects previously screened for this study and/or subjects randomised to treatment who subsequently withdraw cannot re-enter this study.
- 16. Patients participating in any other clinical trial.
- 17. Serious or unstable medical or psychological conditions that, in the opinion of the investigator, would compromise the subject's safety or successful participation in the study.

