3.5 Method of assigning patients to treatment groups

The actual treatment assigned to individual patients will be determined according to a non-centre specific randomisation scheme, which will be produced by AstraZeneca using an AstraZeneca computer software tool, prior to the inclusion of the first patient.

Once a patient has signed the written informed consent form, they will be allocated an enrolment code (e-code) that is a unique identifying number that must be used as the identification number throughout the study. If a patient discontinues from the study, the e-code will not be re-used.

Patients who failed to qualify for the study based on inclusion/exclusion criteria and were not randomised will **not** be allowed to re-enter the study.

The study doctor will establish patient eligibility before treatment randomisation. At Visit 2.1 (Week 0) patients who satisfy the entry criteria will be randomly assigned to receive either rosuvastatin 10 mg, rosuvastatin 20 mg or placebo with a 1:1:1 randomisation ratio. IVRS must be used to randomise the patient. It is important that patients are not randomised ahead of their randomisation visit (Visit 2.1).

At visit 2.1 it is important to check that the medication identification number matches the number allocated by IVRS, prior to treatment dispensation. If a treatment is incorrectly dispensed (i.e., medication identification number does not match the number allocated by IVRS), the error should be rectified and AstraZeneca should be notified as soon as the error is discovered.

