4.8.2 Laboratory safety measurements and variables

4.8.2.1 Methods of assessment

Laboratory analysis will be performed at Visits 1, 2 and 3.

For visit 1, 20ml of blood will be needed. In this visit, lipid profile, glucose, HbA_{1c}, urea, creatinine, reduced hepatic profile (ALT, AST and GGT) and CK will be performed. A TSH analysis will be done and patients with levels ≥ 1.5 ULN will be excluded of the trial. β -HCG will be performed to women with childbearing potential at visit 1.

For visit 2 and 3, 10 ml of blood will be needed. In these visits, lipid profile, apolipoproteins, hsCRP, glucose, urea, creatinine, complete hepatic profile and CK will be performed.

A 10 mL mid-stream urine sample will be collected for analysis at the central laboratory at visits 2 and 3. It will consist of visual description (colour and appearance), a dipstick test (specific gravity, pH, protein (qualitative), haematuria, glucose, ketones, bilirubin and blood), microscopy (red blood cells, white blood cells, bacteria, casts and crystals.

In the event of elevated liver function tests, see Appendix D for guidance with regards to management of elevated liver enzymes.

In the case of new or increased symptoms of muscle pain/myopathy/elevation of CK to >5x ULN developing after randomisation, see Appendix E for guidance with regards to management of increased creatine kinase.

The volume of blood to be collected is detailed in section 4.9.

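### The only pregnancy test is nominally 35 days before study drug is dispensed, so a pregnancy that starts unnoticed in the lead-in meets no scheduled test before dosing

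*Protocol*

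**What the plan says.** Table 1 (section 3.1) ticks β-HCG in the Visit 1 column, week -5, and in no other. The footnote to that row confirms it: an "assay of B-HCG will only be performed at visit 1 for women of childbearing potential". Section 4.8.2.1 agrees that β-HCG "will be performed to women with childbearing potential at visit 1". The blood and urine tests that section 4.8.2.1 lists for Visits 2 and 3 contain no HCG, and Table 1 schedules no laboratory sample at Visit 2.1, where all study drug is dispensed.

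Exclusion 14 in section 3.3.3 covers "Pregnancy, breast-feeding, and women of childbearing potential who are not using a reliable contraception method". Section 9.4 also bars women who are planning a pregnancy. Footnote e to Table 1 says when the criteria must hold: "Patients should fulfil all inclusion criterion with no exclusion criterion to continue in the study during visit 1, 2 and 2.1". Section 3.5 adds: "The study doctor will establish patient eligibility before treatment randomisation". Footnote n to Table 1 ties randomisation to the Visit 2 laboratory work: "Patients will be randomised once the laboratory results from visit 2 are available".

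**The concern.** The Protocol requires that a woman not be pregnant when she is randomised, but it tests for this only about five weeks earlier. Exclusion 14 carries no visit label. Other laboratory-based exclusions are fixed explicitly at entry; for example, criterion 8 reads "Uncontrolled hypothyroidism defined as a thyroid stimulating hormone (TSH) >1.5 times the upper limit of normal (ULN) at Visit 1", and the CK and creatinine criteria are also tied to Visit 1. Even so, CK and creatinine are measured again at Visit 2, as are glucose and the liver tests. β-HCG is not.

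The gap concerns a pregnancy that begins during the lead-in and is unrecognised or not reported. Section 3.1 lists no pregnancy question at Visit 2.1. The adverse-event question in section 4.8.1.2 asks about health problems, and the Protocol does not count pregnancy in itself as an adverse event. After dispensing, the next scheduled visit is week 8, again without β-HCG. Such a woman could therefore take study drug for the whole treatment period without a scheduled pregnancy test, although sections 3.3.5.1 and 9.4 make pregnancy a reason to discontinue.

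**Working it through.** **Inputs, all from the Protocol**

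- Visit 1: week -5, day -35 (section 3.1 and Table 1).
- Visit 2: week -1, day -7.
- Visit 2.1, randomisation and dispensing: week 0, day 0.
- Visit 3: week 8, day 56.
- Windows in section 3.1: ±3 days at Visit 1, ±3 at Visit 2, ±2 at Visit 2.1. Table 1 leaves the Visit 1 window blank.
- Allocation 1:1:1 to rosuvastatin 10 mg, rosuvastatin 20 mg and placebo (section 3.5).

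**Present interval from test to dispensing**

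- Nominal: 5 weeks × 7 = 35 days, which matches the 5-week lead-in of the synopsis.
- With the section 3.1 windows: 35 ± (3 + 2) = 30 to 40 days.
- With only the Visit 2.1 window, as Table 1 shows it: 35 ± 2 = 33 to 37 days.
- One sentence in section 3.1 gives a 4-week lead-in. Read as running to randomisation, it would mean 4 × 7 = 28 days. The week labels -5, -1 and 0 show that four weeks is the distance from Visit 1 to Visit 2, so 35 days is the right nominal figure.

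**Interval if the assay is added at Visit 2**

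- Nominal: 7 days.
- With windows: 7 ± (3 + 2) = 2 to 12 days.
- Reduction: 35 − 7 = 28 calendar days, and 28/35 = 80% of the untested days before dosing.

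**Untested time up to the last visit**

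- Now, Visit 1 to Visit 3: 35 + 56 = 91 days.
- With the added assay, Visit 2 to Visit 3: 7 + 56 = 63 days.

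**Allocation**

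Two of the three arms are active, so 2/3 of any women pregnant at randomisation would be expected to be assigned to rosuvastatin.

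The Protocol gives no sex or age mix and no conception rate, so these intervals cannot be turned into a number of women.

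**The case against.** The best defence is that this is a choice of test frequency, stated consistently in Table 1, its footnote and section 4.8.2.1, and that other safeguards exist. Women of childbearing potential must use reliable contraception, and under footnote e that too must hold up to Visit 2.1. There is a physical examination at Visit 2, a health question at every visit after the first, an eligibility check by the study doctor before randomisation, and discontinuation with outcome follow-up if a pregnancy becomes known. What is left is contraceptive failure or misreported use, within about five weeks, that is also unrecognised or unreported. That is a fair description, and it is why the number affected is likely to be small. None of these safeguards is a pregnancy test, however, so the gap remains.

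The missing visit label on exclusion 14 is only supporting evidence. The HbA1c limb of exclusion 6 is also unlabelled, and HbA1c is measured once. This weakens the comparison with TSH, CK and creatinine, but the requirement in footnote e does not depend on it.

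The 80% is a share of calendar days and not of pregnancies detected. A test does not turn positive immediately after conception, so some conceptions shortly before Visit 2 would also be missed. This limits the benefit of the change but does not remove it.

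Finally, whether HCG can be run on the Visit 2 urine sample depends on a laboratory manual that is not available here. The Visit 2 blood is the alternative if it cannot.

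**Conclusion.** The point holds, as a weakness in the design and not as a contradiction between sections. The last eligibility check before dosing relies on a pregnancy test nominally 35 days old (30 to 40 with the section 3.1 windows), supported by the contraception requirement and by what the patient reports. No scheduled test would find an unrecognised or unreported pregnancy that began in the lead-in. The conclusion rests on the week labels in Table 1 and on the word only in the β-HCG footnote. The Protocol text supplied is incomplete, but nothing in it provides a later test.

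No count of affected women is claimed. Sample size, power and the primary comparison are not materially affected. The change should be made because a possible exposure in pregnancy can be made less likely at very little cost.

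**What to change.** Add β-HCG for women of childbearing potential to the Visit 2 column of Table 1, to the β-HCG footnote and to the Visit 2 test list in section 4.8.2.1. State that a negative Visit 2 result is required before randomisation at Visit 2.1.

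The assay can use the Visit 2 blood draw, or the 10 mL urine sample already sent to the central laboratory at that visit if the laboratory confirms that it is suitable. Urine would add nothing to the 61.5 mL blood limit in section 4.9.

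The cost is one extra assay for each woman of childbearing potential who reaches Visit 2, a subset of the approximately 990 patients expected to enter the lead-in. No visit, needle stick or delay is added, because Visit 2 results are already awaited before randomisation.

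The change does not cover conception shortly before Visit 2, between Visit 2 and dosing, or during the 8 treatment weeks.

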3.2 Rationale and risk/benefit assessment

3.2.1 Rationale for study design and control group

The NCEP ATPIII recommendations for patients with HTG are first to lower the LDL-C levels and then the TG levels in order to reduce the CV risk(2). In HTG patients, a drug that can reduce both parameters will have an additional benefit.

Statins have been shown convincingly to reduce cardiovascular morbidity and mortality in multiple large outcomes trials in various populations, with substantial reductions in LDL-C and TG levels in non-diabetic and diabetic patients (22, 23). Statins reducing TG levels are known to be directly related to the LDL-C reduction potency meaning that more potent statins should be more effective in lowering TG. For this reason, the current study will use one of the most potent statins (RSV) and will test its efficacy in reducing TG levels in Mexican HTG patients.

This study is using a placebo arm as a control. Patients that are currently on statin therapy cannot enter the study because it would not be ethic to stop their statin therapy. As we are using a placebo arm, the study will only last for 8 weeks and all patients will be treated with TLC diet as appropriate. After completing the study period, all patients will be offer to continue with active commercially available therapy determine by the investigator experience.

The 5-week lead in period will serve as a washout period of possible residual effects of preexisting lipid lowering therapy (other than statins) use, which is important to establish a reliable baseline to determine the change from baseline during double-blind treatment.

3.2.2 Risk/benefit and ethical assessment

The identify population for this study are candidate for TLC intervention according to ATPIII guidelines. There is no definition on whether monotherapy with statins will be useful in these patients or not, but there are some evidence on the effect of statins on atherogenic lipid

changes (TG reduction, non-HDL-C reduction, HDL-C increase) and its relation to CV risk reduction (21-23).

This is a placebo control trial and this is the reason why patients with LDL-C \geq 190mg/dL will be excluded from the study because they are candidate to receive statin therapy, so it would not be appropriate to randomise them to the placebo group. All patients entering the trial will be under TLC diet as marked in ATPIII guidelines during all the study period. All patients will be followed during 8 weeks of treatment, and will be offer to continue with an active treatment after study period is concluded as decided by the investigator.

Although the risk of adverse effects with statin therapy exists, there is potential for a greater benefit by reducing TG and non-HDL-C, with the attendant benefit on decreased CV risk in HTG patients. Please refer to the PI for further information about rosuvastatin. All SAEs should be followed until the adverse event has been resolved or stabilised and no further change is expected.

3.3 Selection of study population

3.3.1 Study selection record

Patients may be recruited from primary or secondary care. Centres if appropriate may use advertisements. Investigators must keep a record of patients who were considered for enrolment but were never enrolled e.g., patient screening log. This information is necessary to establish that the patient population was selected without bias.

3.3.2 Inclusion criteria

For inclusion in the study lead-in period at Visit 1, patients must fulfil all of the following criteria:

- 1. Provision of written informed consent
- 2. Male or female aged ≥ 18 years
- 3. Statin naïve patients (as defined by protocol)
- 4. No previous lipid lowering treatment other than statins 6 months before visit 1
- 5. Fasting TG concentrations at visit 1 of: $\geq 200 \text{ mg/dL}$ and < 800 mg/dlL
- 6. Fasting LDL-C concentrations at visit 1 of: $\geq 100 \text{ mg/dL}$ and $\leq 190 \text{ mg/dL}$

(Note: the results of the above laboratory sample will not be available at visit 1 to make the eligibility decision. Therefore, if the subject's medical history meets the eligibility criteria the subject can enter into the dietary lead-in period of the study. However, when the laboratory results are available, if the results do not meet the above criteria, the subject should be contacted and discontinued from the study)

- 7. Fasting TG concentrations at visit 2 of: \geq 200 mg/dL and < 800 mg/dlL
- 8. Fasting LDL-C concentrations at visit 2 of: $\geq 100 \text{ mg/dL}$ and $\leq 190 \text{ mg/dL}$
- 9. Subjects willing to follow all study procedures including the attendance at clinics for scheduled study visits, fasting prior to clinic visits (Visits 1, 2 and 3 blood draws) and compliance with study treatment regimen.

3.3.3 Exclusion criteria

Any of the following is regarded as a criterion for exclusion from the study:

- 1. LDL-C levels \geq 190 mg/dL
- 2. History of any other lipid lowering therapy 6 months before visit 1.
- 3. Subjects considered to be unstable after a myocardial infarction, unstable angina, myocardial revascularisation or a transient ischemic attack (TIA) or stroke
- 4. Subjects awaiting a planned myocardial revascularization prior to starting the study (ie, planned prior to visit 1)
- 5. Severe congestive cardiac failure (New York Heart Association [NYHA] Class IIIb or IV)
- 6. Uncontrolled diabetes diagnosis by $HbA_{1c} \ge 8\%$, or fasten oral glucose $\ge 150 \text{mg/dL}$.
- 7. History of malignancy (unless a documented disease-free period exceeding 5 years is present) with the exception of basal cell or squamous cell carcinoma of the skin. Women with a history of cervical dysplasia would be permitted to enter the study provided they have 3 consecutive clear Papanicolaou (Pap) smears.
- 8. Uncontrolled hypothyroidism defined as a thyroid stimulating hormone (TSH) >1.5 times the upper limit of normal (ULN) at Visit 1. (This is due to the relationship between myopathy and patients with hypothyroidism undergoing statin therapy)
- 9. History of homozygous familial hypercholesterolaemia. (Due to the lipid levels exhibited by this group of patients they are considered unsuitable for this study as they often require combination lipid-lowering therapy)
- 10. History of alcohol, or drug abuse within the last 5 years.
- 11. Current active liver disease [alanine aminotransferase (ALT) (SGPT) > 3 x ULN] or severe hepatic impairment
- 12. Unexplained rise of creatine kinase (CK) \ge 3 x ULN at visit 1

- 13. Serum creatinine > 176 μ mol/L (2.0 mg/dL) at visit 1
- 14. Pregnancy, breast-feeding, and women of childbearing potential who are not using a reliable contraception method.
- 15. Subjects previously screened for this study and/or subjects randomised to treatment who subsequently withdraw cannot re-enter this study.
- 16. Patients participating in any other clinical trial.
- 17. Serious or unstable medical or psychological conditions that, in the opinion of the investigator, would compromise the subject's safety or successful participation in the study.

3.3.4 Restrictions

Patients must comply with the following restrictions during the study:

- 1. Patients will fast (water is permitted) for 12 hours prior to each visit where lipids are to be measured. Patients should also refrain from consuming alcohol and cigarette smoking on the morning of each of these clinic visits (to obtain accurate and consistent results of lipid measurements).
- 2. Patients should be advised to maintain their normal physical activities or exercise (to avoid the effects of changes in physical activity on laboratory measurements, which may risk observation of spurious rises in CK).
- 3. Patients will be expected to follow the NCEP Therapeutic Lifestyle Changes (TLC) diet for the duration of the study (because dietary intake is known to affect blood cholesterol concentration and thus a standard diet is required in studies of lipid-modifying agents).
- 4. Patients should not receive treatment during the study with any of the disallowed medications outlined in Section 3.7 *(for safety reasons and/or to avoid confounding the study results).*
- 5. Concomitant medication is allowed to treat other problems than HTG such as hypertension, CV disease, DM2 and renal disease.

